11.1 Demographic Variables

The demographic variables collected in this study include age, race, ethnicity, and genetic testing results.

Age (years) will be summarized, overall and by group, using continuous descriptive statistics. Age will also be summarized for the following categories: <=12, 13-18, 19-40, and >=41 years. Age will be reported in years and calculated using the following formula:

Age = Integer value of (Date of informed consent minus date of birth)/365.25

The number and percentage of subjects will be presented, overall and by group, for race and ethnicity.

A subject listing that includes all demographic variables and genetic testing results will be provided.

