Enrollment will begin with Group 1A and will proceed to subsequent groups after review of safety data by the DSMC. After review of safety data from Group 1A, participants will be enrolled in Groups 1B and 2 concurrently. After review of safety data from Groups 1A, 1B and 2, participants will be enrolled in Group 3. After review of safety data from Groups 1A, 1B, 2 and 3, participants  $\geq$ 18 years of age will be enrolled in Group 4. As ocular inflammation has been seen in the first 12 subjects enrolled in the study and pediatric participants might be more prone to inflammation, pediatric participants (age 6-17) in this study will first be treated at the middle dose (Group 2A) prior to the enrollment in Group 4.

Within groups 1A, 1B, 2, 2A, and 3, enrollment of participants will be staggered by at least 2 weeks to allow adequate time for review of safety information by the investigators and sponsor.

Within Group 4, enrollment of the first 3 pediatric participants will be staggered by at least 2 weeks to allow adequate time for review of safety information by the investigators and sponsor.

Safety will be monitored by evaluation of ocular and non-ocular AEs, hematology and clinical chemistry parameters and immune responses to RS1.

Efficacy will be measured by evaluation of visual acuity, visual fields, microperimetry, contrast sensitivity, reading speed, OCT with infrared montage, to include volumetric analysis of schisis cavity size, ERG, and quality of life questionnaires.

Other data collected will include fundus photography, immune responses to AAV and the presence of vector DNA in blood.

Approximately 27 participants will be enrolled in this study. Enrollment in this study is anticipated to take approximately 30 months. Enrolled participants will have frequent follow-up visits during the first year after study agent administration.

To monitor for delayed AEs and assess the duration of any changes in visual function or structure that occur, participants will be followed annually for an additional 4 years after the Month 12 visit.

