### 4.1 Subject Inclusion Criteria

Subjects must meet all of the following inclusion criteria to participate in this study.

- 1. Retinal disease consistent with a diagnosis of X-linked retinoschisis and documented mutations in the *RS1* gene (including null mutations and mutations that code for abnormal RS1 protein, except as specified in section 4.2),
- 2. Male individual at least 18 years of age, inclusive (Groups 1A, 1B, 2 and 3), 6-17 years of age, inclusive (Group 2A), or at least 6 years of age, inclusive (Group 4),
- 3. Able to perform tests of visual and retinal function,
- 4. Visual acuity in the study eye not better than:
  - Snellen equivalent 20/80 (58 ETDRS letter score) in the treated eye for Group 1A,
  - Snellen equivalent of 20/63 (63 ETDRS letter score) in the treated eye for Groups 1B, 2, 2A, and 3,
  - Snellen equivalent of 20/50 (68 ETDRS letter score) in the treated eye for Group 4,

The eye with the worse visual acuity will be selected as the study eye. If both eyes have the same visual acuity, the choice of study eye will be determined at the discretion of the investigator in consultation with the participant. ETDRS letter score is the main VA inclusion criterion.

5. Not currently being treated with a carbonic anhydrase inhibitor and not treated with any carbonic anhydrase inhibitor within the 3 months prior to Day 0 (study agent administration).,

- 6. Have acceptable laboratory parameters:
  - Hemoglobin  $\geq$  12.0 g/dL,
  - White blood cell count 3,300 12,000 cells/mm^3,
  - Platelet count 125,000 550,000/mm^3,
  - Alanine aminotransferase (ALT) not higher than 1.5 times the upper limit of the normal range for study laboratory,
  - Serum creatinine not higher than 1.1 times the upper limit of the normal range for study laboratory,
  - Prothrombin time (PT) ≤ 14.5 seconds, inclusive, and partial thromboplastin time (PTT) ≤ 36.0 seconds,
- 7. Be willing to discontinue aspirin, aspirin-containing products, and any other drugs that may alter coagulation, at least 7 days prior to study agent administration.
- 8. Signed informed consent obtained before screening.

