#### 10.7.5 Interim Analyses

Enrollment will begin with Group 1A and will proceed to subsequent groups after review of safety data by the DSMC. After review of safety data from Group 1A, participants will be enrolled in Groups 1B and 2 concurrently. After review of safety data from Groups 1A, 1B and 2, participants will be enrolled in Group 3. After review of safety data from Groups 1A, 1B, 2 and 3, participants ≥18 years of age will be enrolled in Group 4. After review of safety data in Group 2A, the pediatric participants 6-17 years of age may be enrolled in Group 4.

Before each DSMC review, the investigators and sponsor will prepare a summary of all available data. For DSMC reviews related to enrollment in subsequent groups, this summary will include data at least through the visit 2 weeks after study agent administration for all available participants.

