4.1 General Study Design

This is a non-randomized, open-label, Phase 1/2 dose escalation study of the safety and efficacy of rAAV2tYF-CB-hRS1 administered by intravitreal injection in one eye in individuals with XLRS. The primary objective is to evaluate safety and the secondary objective is to evaluate efficacy.

Each participant is to receive rAAV2tYF-CB-hRS1 by intravitreal injection in one eye on a single occasion as outlined in the schematic below.

		Number of Dose Level				
Group ^a	Age (yr)	Subjects	vg/mL	Volume	vg per eye	
1A	≥ 18	3	1.43 × 10 ¹²	0.07 mL	1 × 10 ¹¹	
1B	≥ 18	3	1.43 × 10 ¹²	0.07 mL	1 × 10 ¹¹	
2	≥ 18	3	4.3 × 10 ¹²	0.07 mL	3 × 10 ¹¹	
2A	6-17	Up to 6	4.3 × 10 ¹²	0.07 mL	3 × 10 ¹¹	
3	≥ 18	3	4.3 × 10 ¹²	0.14 mL	6 × 10 ¹¹	
4	≥ 6	Up to 15	MTD ^b	MTD	MTD	

Schematic of Study Design:

^a Visual acuity not better than 58 Early Treatment Diabetic Retinopathy Study (ETDRS) letter score in Group 1A, 63 in Groups 1B, 2, 2A & 3, 68 in Group 4.

^b MTD = maximum tolerated dose determined in Groups 1A, 1B, 2 and 3 for adults, in Groups 1A, 1B, 2, and 3 (adult participants only) and 2A (pediatric participants only) for pediatric participants.

Participants in Groups 1A, 1B, 2 and 3 are at least 18 years of age and receive the vector at a lower dose (Groups 1A and 1B), middle dose (Group 2) or higher dose (Group 3). Participants in Group 1A have visual acuity that is worse than participants in subsequent groups (ETDRS letter score of 58 in Group 1A and 68 in other groups). Participants in Group 2A will be 6-17 years of age and receive the

vector at the middle dose level. Participants in Group 4 will be at least 6 years of age and will receive the vector at the maximum tolerated dose (MTD) determined in Groups 1A, 1B, 2, and 3 for adults; in Groups 1A, 1B, 2, and 3 (adult participants only) and 2A (pediatric participants only) for pediatric participants.

Participants in all groups are selected from individuals who are not being treated with a carbonic anhydrase inhibitor during the study and have not been treated with any carbonic anhydrase inhibitor within the 3 months prior to enrollment in the study. Participants are asked not to begin treatment with a carbonic anhydrase inhibitor within 6 months after study agent administration.

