9.4 Data Analysis Conventions

All data analysis outlined in this SAP will be performed by Statistics & Data Corporation (SDC). Statistical programming and analyses will be performed using SAS[®] Version 9.4 or higher. Output will be provided in Rich Text Format (RTF) for tables and figures and Portable Document Format (PDF) for tables and listings using landscape orientation. All study data for treated subjects will be listed by group, subject, and visit (as applicable) unless otherwise specified. Only a disposition listing will be created for screen failed subjects.

Summaries for continuous and ordinal variables will include the number of observations (n), arithmetic mean, standard deviation (SD), median, minimum, and maximum. Minima and maxima will be reported with the same precision as the raw values; means and medians will be presented to one additional decimal place than reported in the raw values. Standard deviations will be presented to two additional decimal places than reported in the raw values. Summaries for discrete variables will include frequency counts and percentages. All percentages will be rounded to one decimal place (i.e., XX.X%). Change from baseline will be calculated as follow-up visit values minus the baseline value.

All statistical tests will be two-sided with alpha level of 0.05. Unless otherwise specified, summaries will be presented by group (1A, 1B, 2, 2A, 2+2A, 3, 4, 3+4, and all subjects) and, where appropriate, visit.

Unscheduled visits will not be summarized. Study visits will be referred to in all tables and listings with the expected study day/month/year corresponding to the visit to enable reviewers to understand the assessment timing without referring to the protocol visit schedule. The following table shows the scheduled study visits, their planned study day:

Scheduled Visit	Planned Study Day
Visit 1	Screening
Visit 2	Baseline
Visit 3	Day 0
Visit 4	Day 1
Visit 5	Day 7
Visit 6	Day 14
Visit 7	Month 1
Visit 8	Month 2
Visit 9	Month 3
Visit 10	Month 6
Visit 11	Month 9
Visit 12	Month 12
Visit 13	Year 2
Visit 14	Year 3
Visit 15	Year 4
Visit 16	Year 5
1	

10. Disposition of Subjects

The following disposition items will be summarized:

- The number of subjects screened (who signed the informed consent/assent form)
- The number of screen failures
- The number of subjects enrolled (who met the enrollment criteria)
- The number of subjects treated (who received an intravitreal injection of study agent)

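### Planned safety tables never separate children from adults in Group 4, so pediatric safety at the MTD is pooled away if both age classes enrol

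*SAP*

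**What the plan says.** SAP 9.4 sets the default layout for all tables: "Unless otherwise specified, summaries will be presented by group (1A, 1B, 2, 2A, 2+2A, 3, 4, 3+4, and all subjects"). SAP 14.1 then reports TEAEs by group, and the table list in SAP 22 adds no split by age.

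On who enters Group 4, SAP 4.1 states: "Participants in Group 4 will be at least 6 years of age and will receive the vector at the maximum tolerated dose (MTD"). The inclusion criterion in Protocol 4.1 sets the ages as "6-17 years of age, inclusive (Group 2A), or at least 6 years of age, inclusive (Group 4"). Adults enter after the safety review of Groups 1A, 1B, 2 and 3. Children have a separate step in Protocol 10.7.5: "After review of safety data in Group 2A, the pediatric participants 6-17 years of age may be enrolled in Group 4". The MTD is also determined separately. For adults it rests on Groups 1A, 1B, 2 and 3. For children it rests on those groups plus "2A (pediatric participants only) for pediatric participants". The reason for treating children first in Group 2A, given in Protocol 3, is that "pediatric participants might be more prone to inflammation".

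The only age categories that SAP 11.1 sets belong to the demographic summary: "Age will also be summarized for the following categories: <=12, 13-18, 19-40, and >=41 years". The only other age cut in the SAP is at 16 years, for the choice of quality-of-life questionnaire.

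**The concern.** Safety is the primary objective, and the Protocol treats pediatric safety as a question of its own: a separate group, a later entry step into Group 4, staggered dosing of the first three children there, and a separately determined MTD. The SAP follows that logic at the middle dose, where adults (2), children (2A) and both together (2+2A) each have a column. In Group 4 it keeps only the pooled column. A reader of the study report would see one adverse event rate for Group 4 and could not tell from the tables whether the events fell mainly in the children.

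The age bands add a smaller problem. The band 13-18 places an 18-year-old, who is eligible only as an adult, with the 13- to 17-year-olds.

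**Working it through.** **1. Who is in each planned column** (SAP 4.1 and 9.4)

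| Column | Age classes | Dose |
|---|---|---|
| 1A, 1B | adults | lower |
| 2 | adults | middle |
| 2A | children | middle |
| 2+2A | both | middle |
| 3 | adults | higher |
| 4 | both, if both enrol | adult MTD and pediatric MTD |
| 3+4 | both, if both enrol | higher dose, adult MTD and pediatric MTD |
| All subjects | both | all |

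Of the nine columns, only 2A is purely pediatric, and it is fixed at the middle dose. None isolates the children in Group 4. If the pediatric MTD turns out to be the Group 2A dose, column 2A describes children at that dose but leaves out those treated in Group 4.

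**2. Plausible size of Group 4.** Groups 1A, 1B, 2 and 3 take 3 + 3 + 3 + 3 = 12. The group maxima sum to 12 + 6 + 15 = 33, but SAP 6 caps the study at 27. Children enter Group 4 only after Group 2A data are reviewed, so 2A holds at least 1. Group 4 then holds at most 27 - 12 - 1 = 14, or 27 - 12 - 6 = 9 if 2A is full.

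**3. What a pooled cell leaves open.** With N participants in Group 4, k children and x participants affected, the number of affected children can be anything from max(0, x - (N - k)) to min(k, x). The documents do not give k or x, so these values are assumed:

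- N = 9, k = 3, x = 2: the table shows 2/9 (22%); the pediatric rate lies between 0/3 and 2/3 (0% to 67%).
- N = 9, k = 4, x = 4: the table shows 4/9 (44%); the pediatric rate lies between 0/4 and 4/4 (0% to 100%).
- N = 14, k = 5, x = 3: the table shows 3/14 (21%); the pediatric rate lies between 0/5 and 3/5 (0% to 60%).

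**4. Precision of a pediatric sub-column.** The plan's own figures come first. For 0 events in n, the exact two-sided 95% upper limit is 1 - 0.025^(1/n). This gives 33.63% for n = 9 and 12.77% for n = 27, as stated in Protocol 10.5 and SAP 6. The same formula gives 70.76% for n = 3 and 45.93% for n = 6. A pediatric sub-column would therefore be descriptive only.

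**5. Age bands.** Ages 13 and 17 (children) and 18 (adult) all fall in the band 13-18. From the demographic table, the number of children in Group 4 equals the count at 12 or under, plus the count at 13-18, minus the number aged 18. It is exact if no 18-year-old enrols in Group 4, and ambiguous otherwise.

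**The case against.** The strongest reply is that nothing is lost. SAP 9.4 lists all data for treated subjects, SAP 11.1 lists age by subject, and SAP 14.1 lists every AE, SAE and DLT by subject. With 14 or fewer people in Group 4, each event can be matched to an age by hand. Column 2A already gives one purely pediatric result. Pediatric entry to Group 4 is optional, so the gap may never arise. SAP 1 allows supplementary analyses. Sub-columns of 3 to 6 children carry very wide limits.

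All of this is true, and it limits the point to the summary tables. It does not remove it: a listing is not a result, Groups 1A to 3 are already tabulated at n = 3, and column 2A omits the Group 4 children.

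A reader might infer more than the documents support:

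- **That the 13-18 band causes the safety gap.** It does not. The bands appear only in the demographic summary, and changing them would alter no safety table.
- **That the number of children in Group 4 cannot be recovered.** It can, unless an 18-year-old enrols there, and the listings settle it in any case.
- **That all the Protocol's rules divide at 17/18.** They do not. Visual acuity limits and the stagger in Groups 1A to 3 are set by group, the laboratory and exclusion criteria have no age cut, and the DLT pause applies to any participant.

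**Conclusion.** The point holds as a reporting gap in the summary tables for the primary objective. It rests on one condition: both age classes enrol in Group 4. If so, no planned table gives a pediatric safety result for that group, and the pooled cell can be compatible with almost any pediatric rate. If the pediatric and adult MTDs also differ, columns 4 and 3+4 combine two doses as well as two age classes. The documents do not say whether either condition was met, and they give no event counts, so the examples above show only what pooling can conceal. The age-band mismatch is a minor alignment. This is a worthwhile, inexpensive improvement, not a flaw that undermines the safety evaluation.

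**What to change.** In SAP 9.4, add two descriptive sub-columns for Group 4, 6-17 years and 18 years and over, each showing the dose received. Apply them to Table 14.1.2 (demographics), the TEAE tables (14.3.x) and the slit-lamp and indirect ophthalmoscopy shift tables (14.4.5 and 14.4.7), keeping the pooled column as is done for 2, 2A and 2+2A. State what column 3+4 contains if the pediatric and adult MTDs differ.

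Assign participants by the age category under which they were enrolled. SAP 11.1 computes age at consent as whole years of days/365.25, and screening may precede dosing by up to 3 months, so a participant near his 18th birthday could otherwise be misplaced. For example, 6574 days at the 18th birthday gives 6574/365.25 = 17.9986, recorded as 17.

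In SAP 11.1, change the bands to 12 and under, 13-17, 18-40, and 41 and over.

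The cost is SAP wording and extra columns built from data already collected. The Protocol's change log shows that a 12-month analysis has taken place, but AE review continues through Year 5 (Protocol Appendix A), so the final safety tables can still carry the split, identified as an addition in the study report. The downside is small denominators, so the sub-columns should show counts and percentages without tests.

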11.2 Pretreatment Variables

Pretreatment variables include height and weight, clinical variables (temperature, blood pressure, pulse, and respiratory rate), and physical examination results.

11.2.1 Physical Examination

A complete physical examination will be performed at the screening or baseline visit, to include examination of major organ systems (head/eyes/ears/nose/throat, neck, cardiovascular, respiratory, abdomen, musculoskeletal/extremities, skin, lymph nodes, and neurological).

A clinical evaluation, including a symptom-directed physical examination, will be obtained at all other visits.

A subject listing of physical examination abnormalities at baseline will be produced.

11.2.2 Vital Signs

Vital signs, including height, weight and BMI, will be summarized with continuous descriptive statistics at baseline. A subject listing of the vital signs results will also be produced.

12. Medical History and Concomitant Medications

12.1 Medical History

A medical history will be obtained at the screening visit.

A clinical evaluation, including an interim medical history, will be obtained at all other visits.

Medical history will be summarized using discrete summary statistics.

08 August 2017

A listing of medical history will be generated.

12.2 Concomitant Medications

A clinical evaluation including use of carbonic anhydrase inhibitors (CAI) and other medications will be obtained at all post-screening. These medications will be considered concomitant as the data are collected during the course of the study.

Concomitant medications will be coded using World Health Organization (WHO) Drug Dictionary, (Enhanced B2, March 2017) and summarized to the therapeutic drug class (anatomical therapeutic chemical [ATC] 4 classification) and preferred name (generally the brand/trade drug name).

Concomitant medications will be tabulated for each group using frequencies and percentages. Subjects may have more than one medication per ATC text. At each level of subject summarization, a subject will be counted once if he/she reports one or more medications. Percentages will be based on the number of subjects in each group.

Concomitant medications and CAI use will be listed separately.

13. Treatment Exposure

13.1 Treatment Exposure

A subject listing of study agent administration will be produced.

14. Safety Analyses

14.1 Adverse Events

An AE is defined as any untoward medical occurrence associated with the use of a drug in humans, whether or not the event is considered drug-related. An AE can therefore be any unfavorable and unintended sign (e.g., an abnormal laboratory finding), symptom, or disease occurring after the first dose of study drug, without any judgment about causality. Any pre-existing medical condition that worsens after first administration of the study drug will also be considered a new AE. The occurrence of an AE may come to the attention of study personnel during study visits and interviews or by a study recipient presenting for medical care. All AEs must be graded for intensity and relationship to study product.

Every AE recorded in this study must be assessed by the investigator to determine whether or not it meets the definition of a dose-limiting toxicity (DLT). A DLT is defined as any toxicity determined by the investigator to be related to the study agent and deemed serious or sufficiently severe to preclude dose escalation. For the purpose of this study, any grade 4 or 5 event (per the Common Terminology Criteria for Adverse Events [CTCAE] v4.0 criteria) that is assessed as possibly, probably or definitely related to the study drug will be considered to be a DLT.

Treatment-emergent adverse events (TEAE) are defined as any event that occurs or worsens on or after the day that study treatment is administered. AEs which began prior to treatment will not be included in the summary tables but will be included in the AE data listings.

An overall summary will be presented that includes the number of TEAEs and the number and percentage of subjects who experienced at least one TEAE, by group. This summary will also include breakdowns of TEAEs further categorized as ocular (study eye, fellow eye, and both eyes separately) or non-ocular, Grade 3 or 4 local (ocular) or systemic AEs that occur during the 12 months after study agent administration, serious TEAEs (SAEs), TEAEs by maximum severity, TEAEs by maximum relationship to study agent, TEAEs by relationship to study agent injection procedure, and TEAEs leading to subject withdrawal.

Additional summaries of TEAEs will be provided showing the number and percentage of subjects who experienced at least one TEAE. These summaries will be presented by SOC and PT using MedDRA Version 20.0. Non-ocular TEAEs will be summarized by group at the subject level by SOC and PT. Ocular TEAEs will be similarly summarized at the subject level for study and fellow eyes separately. If a subject reports the same PT multiple times within the same SOC, that PT will only be reported once within that SOC. As with the PT, if a subject reports multiple conditions within the same SOC, that SOC will only be reported once. In the summary, SOC will be listed in order of descending frequency for all subjects; PTs will be listed in order of descending frequency for all subjects within each SOC.

Separate summaries will be provided for the following categories of AEs:

- Ocular TEAEs (study eye, fellow eyes, both eyes)
- Non-ocular TEAEs
- Grade 3 or 4 local (ocular) or systemic AEs that occur during the 12 months after study agent administration
- Ocular TEAEs related to study agent
- Non-ocular TEAEs related to study agent
- Ocular TEAEs related to intravitreal injection procedure
- Non-ocular TEAEs related to intravitreal injection procedure
- Serious TEAEs
- Serious TEAEs related to study agent
- Serious TEAEs related to intravitreal injection procedure

All AEs will be assessed by the investigator using the following guidelines to quantify intensity:

- Mild: Events that do not interfere with daily activities and require no medical intervention.
- Moderate: Events that cause some interference with daily activities and may require simple medical interventions.

08 August 2017

- Severe: Events that prevent usual daily activities and require medical intervention.
- Life-threatening: Any adverse drug experience that places the subject, in the view of the investigator, at immediate risk of death from the reaction as it occurred, i.e., it does not include a reaction that had it occurred in a more severe form, might have caused death.
- Fatal: Any AE that causes the death of the subject. Except for sudden and unexpected death, death is not an AE, but rather the event that caused the subject to die is the AE.

Summaries of TEAEs by maximum intensity will be presented for ocular AEs and non-ocular AEs separately. The number of subjects with any TEAEs (along with percentages) will be tabulated by SOC and PT within each SOC by treatment group. To count the number of subjects with any TEAEs, if a subject has multiple TEAEs coded to the same PT within the same SOC, the subject will be counted once under the maximum severity.

The relationship of each AE to the study drug/intravitreal injection procedure should be determined by the Investigator using these explanations:

- Associated The event is temporally related to the administration of the study agent/ intravitreal Injection procedure and no other etiology explains the event.
- Not Associated The event is temporally independent of study agent intravitreal Injection procedure and/or the event appears to be explained by another etiology.

Events assessed as being associated with the study agent or associated with the intravitreal injection procedure will be further classified as possibly, probably or definitely related to study agent or injection procedure.

Events assessed as being not associated with study agent or injection procedure will be further classified as probably not or definitely not related to study agent or injection procedure.

All AEs will be presented in a by-subject listing. AEs leading to study treatment discontinuation, all serious AEs, and DLTs will also be presented in separate listings.

